Biplane Fluoroscopy and CT scans: There is a very small increased risk of cancer due to the amount of radiation exposure involved in this study. Based on previous Radiation Safety Applications by our research group, and using conservative estimates, the estimated radiation exposure is from up to three sources the CT scans of subject anatomy (a) traditional CT, (b) LineUP CT and (3) three visits to the biplane fluoroscopy laboratory. For risk (a) the traditional CT imaging is conservatively estimated to expose participants to 0.20 mSv of ionizing radiation (b) the LineUP CT imaging is conservatively estimated to expose participants to 0.10 mSv of ionizing radiation and for the fluoroscopic exposure (c) an estimate (again conservative) of 0.21 mSv for 80 biplane trials. The total estimate of exposure for the whole study is 0.51 mSv. The upper limit of radiation exposure involved in this study is approximately ~16.5% of the estimated naturally occurring background radiation exposure (of 3.1 mSv) (<http://hps.org/documents/>) "Background Radiation Fact Sheet." For additional comparison, the EPA (<https://www.epa.gov/radiation/radiation-sources-and-doses>) estimates of annual radiation exposure is 6.20 mSv (3.1 mSv from naturally occurring background radiation and 3.1 mSv man-made sources such as equipment used in medical procedures), this study will therefore expose participants to ~8.2% of the annual background radiation. Please note that this is the maximum anticipated exposure, in practice we find that participants normally complete their walking trials in well under 80 attempts (45 trials would be the minimum required), but we wish to be conservative with our

estimate. We will minimize the risk due to radiation by taking the minimum number of traditional CT scans, LineUP CT scans, and fluoroscope trials needed to obtain the necessary data. This means that some participants may only require 1 traditional CT scan, 8 LineUP CT scans (vs. up to 15), and 45 trials (vs. up to 80). It is anticipated that most participants, particularly controls, will be well under the maximum of 1 CT scan, 15 LineUP scans, and 80 exposures we have budgeted for in our radiation estimate.

Participants may be exposed to loud noises (like a heavy door slamming) when they are inside the building that houses the biplane fluoroscopy lab; this may startle some individuals. The building where lab is located also houses a blast machine. The blast machine is located in a separate lab, diagonally across the building from the biplane fluoroscopy lab. The blast machine can be quite loud when standing directly outside of the door of the lab where it is located, however when walking to or when inside the fluoroscopy lab the noise sounds like a muted bang/door slamming. We have a set of standard operating procedures that will be followed in order to minimize the risk that participants will be exposed to noises from the blast machine. The SOPs include escorting participants at all times and informing them of the potential noises prior to entering the building.

Biplane Trip and Fall: There is a risk of tripping and falling while walking on the Biplane imaging walkway. The the biplane imaging walkway is clear of obstacles and is level, dry, and rigid. Thus, walking on the biplane walkway is akin to walking on a well-maintained sidewalk. The biplane walkway also has support railings on both sides; these railings will be within easy reach of participants at all times. Participants will also have time to familiarize themselves with the shoes and the area in which they will be asked to walk.

Stress and Inflicted Insight: Participants may feel a mild level of emotional stress if they find it inconvenient to travel to the VA for study visits, or if they have difficulty sitting or standing still during the CT scan. It is possible that we could discover that female participants are pregnant. It is also possible that the imaging procedures (CT scans, and fluoroscopic images) could reveal that a participant has a serious health problem or anatomical abnormality (e.g., bone cancer). Potential participants will be screened during the telephone call, or in person screening, regarding their willingness to be made aware of the pregnancy test result and/or potential health problems discovered by the imaging procedures. Those who are not willing to be told about this information will be excluded from the study. Additionally, in the consent form, participants will again be made aware of this possibility and given the option to decline participation in the study if they choose. If a participant is determined to be pregnant and/or if we see an unexpected abnormality in a participant's radiological images we will advise them to follow up with their regular health care provider.

Wearing Study Assigned Footwear and the StepWatch

At Home Trip and Fall: There is a risk of tripping and falling while wearing the study assigned footwear at home and in the community, but this risk is not greater than that of daily life.

Increased Foot or Ankle Pain, Soft Tissue Irritation: There is a risk that the study assigned footwear could increase foot or ankle pain. There is a risk of minor discomfort, soft tissue irritation or skin break down (e.g. skin blister) in response to wearing the study assigned footwear and the SAM. Participants will be instructed to inform us if they feel discomfort or pain when wearing the control shoes, RB shoes, or AFO for the first time. Participants will have the opportunity to walk around to

confirm the shoe or orthosis fits them well and is comfortable before taking them home. Participants can change the size of the shoe or orthosis to achieve the best fit. The acclimation periods will give participants time to adjust and respond to the footwear which will minimize the risk of soft tissue irritation or discomfort. If proper fit and comfort cannot be achieved the participant will have the option to wear their own preferred footwear for a period of time or they can withdraw from the study. We may opt to move the participant to the next footwear condition after a washout period, if the participant wishes to continue in the study. Participants will be instructed to either drop out of the study or follow up with their regular clinician if they experience an increase in foot/ankle pain that concerns them (vs. their typical pain level) while wearing the study footwear. We will be regularly monitoring pain ratings throughout the study so participants will be aware of their pain and if it is changing significantly. If proper fit and comfort cannot be achieved the subject will have the option to wear their own preferred footwear for a period of time or they can withdraw from the study.

Quality Control

The PI will ensure the study procedures are being properly followed by keeping the research staff well informed of the current study procedures through regular/ongoing contact and meetings. The PI and/or designated research staff will verify visually that the data are sufficient and accurate as soon as possible after each data collection visit is complete.

Privacy and Confidentiality

See section 7.0 below for Information Security, Privacy and Confidentiality related procedures.

5.6 Data Analysis

Means and SDs of daily step count, numeric pain rating, self-selected walking speed, PROMIS, AAOS-FAM, and FAOS survey scores will be calculated in MATLAB for each intervention (control shoe, RB shoe, AFO). Sagittal, frontal, and transverse plane ROM for the talocalcaneal, talocrural, talonavicular, naviculocuneiform, and the first cuneometatarsal joints will be defined as the difference between the maximum and minimum angular joint position in the sagittal, frontal, and transverse planes during the stance phase of gait. Means and SDs of ROMs will be calculated in MATLAB.

Anatomical Coordinate Systems for ROM Calculation:

In order to determine joint motion, we first must assign anatomical coordinate systems to the bones. To accomplish this in a repeatable manner, we employ a template-matching algorithm to embed anatomical landmarks onto each bone. This is done by “morphing” a standard foot geometry template onto a given subject’s bony anatomy. The selected template foot was verified to be free of bone deformities and image/object artifacts by a group consisting of engineers and an orthopedic surgeon. Using a custom graphical user interface (GUI), the landmarks were located and embedded with digital markers to determine the spatial positions. The template foot can then be registered to all of the feet in the study.

Example – Talocrural Coordinate Systems for ROM Calculation:

Three landmark points ($P1$, $P2$, and $P3$) are used in defining the coordinate systems for the tibia/fibula (the tibia and fibula are grouped together) and talus. The first directional unit vector \vec{n}_1 is computed from the vector between $P1$ and $P2$. A dummy vector \vec{n}_d is calculated from $P2$ and the

last point $P3$. The cross product between $\vec{n1}$ and $\vec{n2}$ yields the second directional unit vector, $\vec{n3}$. Finally, the cross product between $\vec{n2}$ and $\vec{n3}$ yields the final directional unit vector $\vec{n1}$.

Talar landmarks: Landmark points for the talus were located at the lateral point of the talar head ($P1$), posterolateral (trigonal) process of the talus ($P2$), and medial point of talar head ($P3$). The direction unit vectors were calculated in the y, z, x order (Figure 8).

Tibia/Fibula Landmarks: Landmarks are placed on both bones to define their coordinate system. The landmarks are placed at the: lateral superior point of the Fibula ($P1$), lateral malleolus ($P2$), and medial malleolus ($P3$) while the order of calculation of the direction unit vectors were z, y, x ($\vec{n1}, \vec{n2}, \vec{n3}$) (Figure 8).

[figure not shown]

Figure 8: Template talus (left images, lateral view for top image, superior view for bottom image) and template tibia/fibula (right image pair, lateral view for left image, posterior view for right image). Landmark points are shown as black dots on the bone surface. Anatomical axes derived from landmark point locations are also shown (red, blue, green arrows).

Template Matching:

To register the template bones onto a study subject's bones, the template bone is first aligned to the subject bone by a rigid body registration and an affine transformation (i.e., uniform volumetric scaling to the template bone). The principal axes, obtained from a principal component analysis, and center of volume (COV) for both the template and subject bone are used to estimate the initial transformation parameters for the registration of the template bone to the subject bone. That is, the two bones are initially aligned along their principal axes, and isometrically scaled to have the same volume. At this point the template is roughly aligned and a similar size as the subject bone. To further match the template with the target, non-rigid B-spline registration was used to deform the template further onto the subject bone. This registration yields a deformation field of three-dimensional vectors defining the displacement of points on the template to the corresponding points on the subject bone.

Landmark Transformation:

The final step uses the registration results to perform a point mapping from the template to the subject bone. Using the affine transformation matrix (T) and the deformation field (d) points, points (x, y, z) on the template can be mapped directly to corresponding points (x', y', z') on the subject. This formula is applied to the key anatomic landmark points on the template bone (i.e., points $P1, P2,$ and $P3$ above), to determine their corresponding location on the subject bone. These transformed landmarks thus define the bone-embedded coordinate system

This process establishes a tibial anatomical coordinate system and a talar coordinate system for measuring talocrural joint ROM. These same methods will be used to measure talonavicular, naviculocuneiform, and the first cuneometatarsal kinematics. By performing this template matching algorithmically, we can ensure consistency in post processing of anatomical coordinate systems between subjects.

Statistical Methods:

For **Specific Aim 1**, linear mixed effects regression will be carried out to test for differences in mean step count, self-selected walking speed, physical function or pain (the dependent variables) by intervention, (control shoe vs. RB shoe vs. AFO, the independent fixed effect) with study subject as a random effect. If the omnibus test for the association between outcome variables and intervention is significant, pairwise comparisons will be carried out to assess differences in mean outcomes between the RB shoe or the AFO and the control shoe (Hypothesis 1.1) and between the RB shoe and the AFO (Hypothesis 1.2).

For **Specific Aim 2**, linear mixed effects regression will be used as above to examine differences in mean [sagittal plane] ROM (the dependent variable) by intervention (control shoe, RB shoe, AFO; the independent fixed effect) with subject and subject by intervention interaction as random effects. If the omnibus test for association between [sagittal plane] ROM and foot intervention is significant, pairwise comparisons will be carried out to assess differences in mean [sagittal plane] ROM between the RB shoe, the AFO, and the control shoe (Hypothesis 2.1). Secondary analyses will be carried out using methods similar to those described above to determine if the interventions affect frontal and transverse plane joint ROM.

For **Specific Aim 3**, hypotheses 3.1 and 3.2, the above model will be modified with the definition of the independent fixed effect, foot intervention, having an additional category representing the healthy control group. Post-hoc comparisons will focus on differences in mean step count, self-selected walking speed, physical function, pain or [sagittal plane] ROM between RB shoe or AFO and the healthy control subjects wearing the control shoes. Additional secondary analysis will be carried out using linear mixed effects regression to determine if pain (the dependent variable) correlates with [sagittal plane] ROM (the independent fixed effect, averaged over trial) and step count (the dependent variable) correlates with pain (the independent fixed effect) with study subject as a random effect in both sets of models. To determine if the mean differences in outcome by intervention (AFO vs. RB shoe) varies by OA severity, the regressions described above will be modified by adding two additional independent co-variates: OA severity and OA severity X intervention. The significance of the latter interaction term suggests that OA severity may influence outcome differences by intervention.

Power Analysis:

Ten thousand datasets were generated using mean [sagittal] ROM for the control foot of 15.3 degrees, between subject SD of 2.0 degrees, and within subject SD of 2.4 degrees.⁸⁴ Power was estimated for sample sizes of 15 and 20 subjects and for a 1.5 degrees and 2.0 degrees difference in [sagittal] ROM between the control shoe and the RB shoe or AFO. Hypothesis testing for each bootstrapped sample for the reduction in ROM was carried out using a linear mixed effects regression of [sagittal] ROM (the dependent variable) on foot (ROM or AFO vs. control) with study subject and subject by intervention interaction as random effects. Power was estimated by determining the number of tests that were significant at the 0.05 level using the likelihood ratio test. The analysis indicated that if the footwear induces a 1.5 degrees change in ankle [sagittal] ROM then a sample size of 20 or 15 subjects results in 94% or 84% power, respectively. If the change in ROM is 2.0 degrees, then even with only 15 subjects the study has 98% power (Table 2). Note that we expect the change in [sagittal] ROM to be significantly more than 1.5 degrees but even for this small difference our study is adequately powered with 25 subjects. Based on these results, we plan to enroll 30 subjects into the

study and expect several to drop out leaving a sample size of at least 25 subjects and the study power greater than 94% (Table 2).

Simulated [sagittal] ROM difference between the control shoe and RB shoe or AFO	Number of subjects	Estimate power
1.5 degrees	15	84%
2.0 degrees	15	98%
1.5 degrees	20	94%

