SA 3: Compare the ankle OA clinical and biomechanical outcome measures for the control shoe, RB shoe, and AFO to a healthy control group wearing control shoes. This will determine the difference in clinical and biomechanical outcomes related to the presence of OA.

Methods: We will enroll 100 participants with ankle OA and 50 control participants without lower limb pain. Three study groups will participate in this project. Study group 1 is a single day study and have images taken using our biplane fluoroscopy system. Study group 2 is a three month take home, and Study group 3 is a three month take home and will have images taken using our biplane fluoroscopy system. At visit-1 all participants will do baseline measures (questionnaires and functional assessments, including **SSWS**) and have a CT scan. During the initial visit, group 1 will participate in a biplane assessment. Participants in Study group 2 & 3 will be assigned to a randomly selected order of footwear (RB shoe, control shoe or an AFO). Each footwear condition will be worn for a three-week trial period at-home/in-community (one-week acclimation, two-weeks continuous wear). Participants will complete brief weekly pain assessments and wear a step counter. At visit-2 participants will do a pain rating, repeat the questionnaires and SSWS test, and group 3 will have images taken using our biplane fluoroscopy system. Participants will continue wearing the step-counter during a one week washout period. For the next three weeks, participants will repeat the at-

home/in-community procedures (step counter, weekly pain rating) and come to the VA to repeat the visit-2 procedures. The same process will be repeated for the third footwear condition.

List of Abbreviations

Provide a list of all abbreviations used in the protocol and their associated meanings.

AE - adverse event

AFO - ankle-foot orthosis

CT - computed tomography

mSv - millisievert

OA - osteoarthritis

RB - rocker bottom

ROM - range of motion

ROP - report of other problem

SAE - serious adverse event

SSWS - self-selected walking speed

UW/HMC - University of Washington/Harborview Medical Center

Contents

Protocol Title: Do Rocker Bottom Shoes and Ankle-Foot Orthoses Reduce Pain and Improve Mobility for Ankle Osteoarthritis Patients?..... 6

1.0 Key Study Personnel..... 6

2.0 Introduction..... 6

3.0 Specific Aims and Hypotheses..... 7

4.0 Resources and Personnel..... 8

5.0 Study Procedures..... 8

 5.1 Study Design..... 8

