We will take video and photos of participants during portions of this study for documentation and use in research publications. All videos and photos will be anonymized (to avoid facial or voice identification) and tattoos and other distinguishing marks will be covered before images are captured or obscured during processing to protect the identity and privacy of our participants.

During study sessions, visitors and observers will not be allowed in the lab unless the participant agrees to their presence; the participant can change her/his mind at any time.

Study Footwear

Over the course of the study (one day or ~3 months) participants will be asked to wear up to three different footwear conditions: control shoes (a typical walking shoe, such as the New Balance 928), RB shoes (walking shoes with a front-to-back curved sole, such as the New Balance 928 with a rocker sole), and an orthotic device (such as an AFO, an ankle brace, such as the Toeoff[®] AFO) with control shoes. Participants will wear each footwear condition, in a randomized order. For all footwear conditions a fitbit zip may be clipped or taped to the shoe. This will record steps taken in the footwear. The fitbit will be synced during the VA visits and will only record number of steps. A separate account for each fitbit will be created and the account number will be recorded on the participant crosswalk. There will be no additional methods to link the data to the participant. Additional assessments on the initial day may include barefoot and own shoe as footwear conditions.

Screening /Eligibility Verification

Participants will have been preliminarily screened during recruitment, then during the first visit, after informed consent, we will make a final eligibility determination. This will include verifying that the information collected during recruitment is accurate and current.

If a participant cannot continue in the study, they will be compensated \$50 for the visit.

Demographic Data collection

Participants' age, sex, race/ethnicity and Veteran status will be recorded.

Anthropometrics

Participants' weight, waist circumference, and height will be measured.

Pain/health screening

Short survey which will include questions regarding trauma history in the lower limbs, joint replacements, OA, and pain throughout the body.

Functional Assessments

Self-selected Walking Speed (SSWS)

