Over the course of the study, participants with ankle OA will repeat the biplane fluoroscopy session 3 times (once for each footwear condition). Participants in study group 1 will complete the biplane in one session while barefoot, or wearing their own shoes, the control shoes, RB shoes, and/or the AFO. Each participant will receive no more than 80 total biplane imaging trials as part of the study.

Participants enrolled in study group 3 will continue wearing the StepWatch. Those in study group 1 have completed their participation and will return the study footwear and StepWatch.

Take home study

Length of participation

For participants with ankle OA, study procedures will occur over ~3 months (11 weeks). Four study visits will be done at the VA Puget Sound where three at-home/in-community study footwear (control shoes, RB shoes, an AFO) condition periods will be conducted.

Visits at the VA Puget Sound may last up to 4 hours each. Participant schedules and the accessibility of facility resources may extend the study timeframe beyond these estimates. Study visits will be scheduled by contacting the participants on phone, or during in-person contacts. We may contact participants with appointment and/or at home activity reminders via email or phone.

Assessment 1

During this initial assessment participants will complete the, Screening, Functional assessments, LineUP with pregnancy test (not Study group 4), Questionnaires, and Brief Pain Rating. Participants will be given a StepWatch and the first footwear condition. At the first assessment, participants who elect to use Ilumivu will be assigned a randomized username for the ilumivu mobile application. The link between this unique ID and the Veteran's identity will not be stored in the mobile application, but rather, stored locally at the Seattle VA. Further information about data security can be found in the Data Security section of this application. Ilumivu, is an app downloaded onto your phone. This app and its developers do not have any information that can be linked back to the participant. Only the researchers will know the Ilumivu participant ID. The Ilumivu participant ID will be recorded on the participant crosswalk in the research folder on the R drive. There will be no additional methods to link the data to the participant.

In Home/Community - Footwear Condition 1: Acclimation and Continuous Wear Period (3 weeks)

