On day-1 of the first at home period, participants will wear the study footwear for one hour, then for two hours on day-2, three hours on day-3, then continue adding one hour of wear per day until the seventh day is reached. For the next two weeks, participants will wear the study footwear throughout the day during their normal daily activities. Participants will wear the StepWatch throughout this 3-week period. Each day participants will receive two messages either via email or with Ilumivu from the study staff, one in the morning, reminding the participant to wear the selected

footwear for the suggested number of hours, and one in the evening, reminding the participant to record the number of hours he/she has worn the selected footwear.

Once per week we will call/email/ message through Ilumivi (which ever the participant prefers) participants to check in and complete the Brief Pain Rating and Qualitative assessment.

Participants will be instructed to contact us if they have questions or if the study footwear is painful/uncomfortable. We will address any issues on an as needed basis, which may require additional visits to the VA.

If a proper and comfortable fit cannot be achieved with a footwear condition, then participants may wear their own shoes for a one-week washout period (while continuing other study procedures) and we will move them to the next footwear condition if they wish to continue their participation. If we determine that it is not in the participant's interest to continue in the study he/she will be withdrawn.

Assessment 2

After the 2-week continuous wear period, participants will come to the VA Puget Sound with the StepWatch and study footwear. The StepWatch data will be downloaded and participants will complete the Brief Pain Rating, Qualitative assessment, Questionnaires, and Functional assessments. For those enrolled in Study group 3, the Biplane assessment will be conducted during this visit using the current footwear condition.

Participants will be given instructions for the second footwear condition.

In Home/Community Footwear Condition 1 Washout Period (1 week)

For the next week, participants will be asked to wear their own self-selected footwear, continue wearing the StepWatch and complete the weekly pain rating over the phone.

In Home/Community – Footwear Condition 2: Acclimation & Continuous Wear Period (3 weeks)

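### Cheap improvement: the Aim 1 and Aim 2 models for the randomised three-period footwear crossover have no period term, so any drift over about 11 weeks costs precision

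*Combined protocol and SAP*

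**What the plan says.** Section 5.5 (Study Footwear) states: "Participants will wear each footwear condition, in a randomized order". The Abstract says the same for study groups 2 and 3. The Take home study text gives three 3-week wear periods and two 1-week washouts: 3 × 3 + 2 × 1 = 11 weeks. End-of-condition assessments therefore fall at about weeks 3, 7 and 11, so the first and last are about 8 weeks apart.

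Section 5.6 (Statistical Methods) compares the Aim 1 outcomes "by intervention, (control shoe vs. RB shoe vs. AFO, the independent fixed effect) with study subject as a random effect". It compares Aim 2 ROM "by intervention (control shoe, RB shoe, AFO; the independent fixed effect) with subject and subject by intervention interaction as random effects". Aim 3 reuses the model, with footwear "having an additional category representing the healthy control group". The only covariates added anywhere are OA severity and its interaction with intervention, in a secondary analysis. Period, order and sequence appear neither in the analysis methods nor in the power calculation, and no balancing of the footwear orders is described.

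**The concern.** In a crossover, a subject's three values differ because of footwear, random variation and whatever changes with calendar time or repeated testing. The documents give some reason to expect a time component: the Abstract calls the disease progressive, and the walking tests and questionnaires are repeated at every assessment. The one-week washout is aimed at carry-over and does not remove drift.

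Without a period term, drift is counted as unexplained within-subject variation. In Aim 2, with several trials per condition, it is absorbed mainly by the subject-by-intervention variance, which is the error term for the footwear contrast. Intervals widen, and the omnibus test that must be significant before Hypotheses 1.1, 1.2 and 2.1 are examined loses power. Aim 1 has no power calculation to show that it could absorb such a loss.

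**Working it through.** **Assumed inputs.** Linear drift of d within-subject SDs per period; n = 24; AFO minus control = 0.83 SD, chosen to give about 80% power without drift.

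**Aim 1, balanced orders.** Period is orthogonal to footwear, so the estimated contrast is unaffected and its true SE is √(2/24) = 0.289 SD. The drift adds a sum of squares of 24 × 2d² = 48d², which the planned model leaves in an error term with 72 − 24 − 2 = 46 df. The estimated SE is therefore inflated by √(1 + 48d²/46).

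- d = 0.25: √1.065 = 1.03
- d = 0.5: √1.261 = 1.12
- d = 0.75: √1.587 = 1.26

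Power without period is about Φ(0.83/0.289 − 2.013 × inflation). At d = 0.5 this is Φ(2.875 − 2.260) = 73%. At d = 0.75 it is Φ(2.875 − 2.536) = 63%. Simulation of the AFO–control t test agrees:

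| Drift per period (SD) | Balanced orders: without vs with period | Simple random orders: without vs with period |
|---|---|---|
| 0 | 80 vs 80% | 81 vs 78% |
| 0.25 | 78 vs 80% | 78 vs 79% |
| 0.5 | 73 vs about 80% | 72 vs 79% |
| 0.75 | 63 vs 80% | 62 vs 79% |

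The omnibus test loses as much: 73 vs 83% at 0.5 SD and 61 vs 82% at 0.75 SD (balanced orders). Without period, type I error stays near 5% with random orders and falls to about 2% or below at 0.5 SD and above with balanced orders.

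**Dependence on n.** At n = 60 the inflation at d = 0.75 is √(1 + 120 × 0.5625/118) = 1.25, so the widening is about the same. The power loss shrinks if power is already high. For the same 0.83 SD effect, power is Φ(4.546 − 1.980 × 1.254) = 98% without period and Φ(4.546 − 1.981) = 99% with it.

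**Aim 2, anchored on the plan's power figures.** Section 5.6 gives a within-subject SD of 2.4 degrees and powers of 84% (n = 15, 1.5 degrees), 94% (n = 20, 1.5 degrees) and 98% (n = 15, 2.0 degrees). The number of trials per condition behind these is not stated. With m trials, SE = 2.4√(2/(nm)). Taking m = 3 gives 84.2, 92.8 and 97.7%, within 2 points of all three, so three trials is a workable assumption. The SD of a condition mean is then 2.4/√3 = 1.39 degrees. Solving the stated powers directly for the SD of a paired difference gives 1.79 to 1.97. Divided by √2, that is 1.27 to 1.39 degrees.

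For a 1.5 degree effect, n = 24, SD 1.39 and balanced orders, power without vs with period is:

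- no drift: 95.8 vs 95.9%
- 0.5 degree per period: 93.9 vs 95.6%
- 1.0 degree per period: 88.1 vs 94.8%
- 1.5 degrees per period: 76.4 vs 95.0%

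At SD 1.28, drift of about 1 degree per period gives 93 vs 97%.

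**Unbalanced realised orders.** With simple random orders and 1.5 degrees per period, the empirical SD of the Aim 2 contrast without period rises from 0.41 to 0.58 degrees. With period it stays at 0.41.

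**The case against.** The strongest reply is that this is an optional efficiency gain resting on an assumed quantity. No document reports drift, and at or below 0.25 SD per period the gain is negligible. The choice n = 24 with 0.83 SD puts power at 80%, where it is sensitive to extra error. The Power Analysis expects at least 25 evaluable subjects, while Section 5.1 targets 100 people with OA without splitting them by study group, so Aim 1 may be larger. For Aim 2, a drift of 1 degree per period means 2 degrees from first to last assessment, which nothing in the documents predicts. Study group 1 has no 11-week drift at all: "Participants in study group 1 will complete the biplane in one session".

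All of this stands as a limit on size. It does not remove the point, because the proportional widening hardly depends on n and the remedy is nearly free.

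Three stronger readings are tempting, and the documents do not support them.

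- A reader might infer that the footwear comparison is biased or that false positives are inflated. Randomised order prevents both.
- A reader might infer that the order worn departs from the order assigned, because after a poor fit "we will move them to the next footwear condition if they wish to continue their participation". That text supports a condition being abandoned, not a changed sequence.
- A reader might infer that the Aim 3 comparison with healthy controls is already distorted. The current Aim 3 model has no period term, so no such shift arises from it. It could arise only from adding period carelessly.

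**Conclusion.** The omission is real, and correcting it is a cheap improvement rather than the repair of an error. The planned tests are valid, or conservative with balanced orders. What is at stake is precision: for Aim 1, intervals 3, 12 and 26% wider at drifts of 0.25, 0.5 and 0.75 SD per period, and at n = 24 a loss of about 2, 7 and 17 points of power (80% with period against 78, 73 and 63% without). These figures assume linear drift, balanced orders and complete data. The drift, the Aim 1 sample size and the Aim 1 effect are all assumptions. If drift is small, almost nothing is lost. For Aim 2 at the planned size the benefit is small unless drift approaches 1 degree per period.

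**What to change.** In Section 5.6, add period (1, 2, 3) as a categorical fixed effect in the Aim 1 model for every outcome and in the Aim 2 model for study group 3. Define period as the assigned slot in which the footwear was worn, and keep that slot number when an earlier condition was abandoned.

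One caution belongs with the change. Where Aim 3 reuses the model, code period as sum-to-zero contrasts for OA take-home participants and as 0 for healthy controls, and also as 0 for any single-session study group 1 rows. The comparison with controls is then averaged over periods. If controls were instead left at reference period 1, the contrast would shift by one drift unit. In a mixed-model check with drift of 0.5 SD and a true AFO–healthy difference of −0.20, the mean estimate was −0.20 with sum-to-zero coding and −0.74 with controls at period 1 (simulation SE 0.04).

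The cost is SAP wording, keeping the period slot in the analysis dataset, and two degrees of freedom (46 to 44 at n = 24). If there is no drift, that is about 0 points of power with balanced orders, or about 2 to 3 points with simple random orders at n = 24. No visit or measurement is added.
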